5.9.1 Prohibited Medications and Therapies

Use of any GABAergic agents (e.g., acamprosate, baclofen, vigabatrin, tiagabine and riluzole) on a regular schedule is prohibited from the time informed consent is obtained to the end of a study participant's participation in the study. Sodium oxybate is also prohibited. Study participants who entered the study on a stable dose of gabapentin (i.e., stable dose for at least 4 weeks prior to randomization), may continue on the treatment as long as no dose modifications are expected during the study. Any change in gabapentin dose during the study must be captured and documented as a protocol deviation.

Use of benzodiazepines, zolpidem, zaleplon, zopiclone, eszopiclone, barbiturates, or ramelteon for sleep is prohibited within the 4 weeks prior to Day 1 or during the study. Benzodiazepines administered as needed or as a regularly scheduled dose for indications other than insomnia (e.g., seizures, anxiety) are permitted. Minocycline and levodopa are prohibited from 4 weeks prior to Day 1 to the end of a study participant's participation in the study.

Use of other investigational agents (e.g., products without market authorization [approved label]) is prohibited during the study.

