OV101 is the first highly selective, extrasynaptic gamma-aminobutyric acid (GABA) receptor agonist that binds orthostERICALLY to the δ -subunit of extrasynaptic GABA receptors. The mechanism of action of OV101 is unique among GABAergic agents, including benzodiazepines, zolpidem and other zolpidem-like drugs, neurosteroids, and drugs that act on GABA metabolism or uptake. Research has shown that absence (or dysfunction) of *UBE3A* results in an aberrant increase in the uptake of GABA, which is the main inhibitory neurotransmitter in the brain. OV101 is the first highly selective GABA receptor agonist that acts on $\alpha 4\delta$ -containing GABA A-receptors. These receptors mediate tonic inhibition and sleep maintenance. In a mouse model of AS, OV101 was shown to restore tonic inhibition in *UBE3A*-deficient cerebellar neurons and

correct motor abnormalities in UBE3A-deficient mice (Egawa et al 2012). These results suggest that OV101 may alleviate the motor dysfunction observed in individuals with AS. Importantly, OV101's ability to potentiate tonic inhibition is unlike any other GABAergic agent, including benzodiazepines, zolpidem, zaleplon, zopiclone, barbiturates, neurosteroids, and drugs that act on GABA metabolism or uptake. In addition to the data on presynaptic dysfunction leading to reduced tonic inhibition, there are additional studies which speak to the potential of OV101 in AS, including modulation of sleep and cognition domains that are impaired in study participants with AS (Ramamoorthi and Lin 2011; Brickley and Mody 2012; Egawa and Fukuda 2013; Deidda et al 2014; Berry et al 2015; Dissel et al 2015).

Phase 2 and Phase 3 studies in adult study participants with primary insomnia demonstrated that OV101 is effective in restoring classical sleep parameters (sleep induction and sleep maintenance) and slow wave sleep, resulting in an improvement in the quality and restorative effects of sleep.

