4.1.1 Inclusion Criteria

Each study participant must meet all the following criteria to be enrolled in this study:

1. Ovid study enrollment criteria:
 - Has completed the OV101-15-001 or OV101-16-001 study up to the EOS, or
 - Has completed the OV101-19-001 study up to the EOT, or
 - Is a sibling of a study participant with AS who has completed OV101-15-001, OV101-16-001, or OV101-19-001.
2. Has a previous diagnosis of AS with molecular confirmation.
3. Is at least 2 years old and has a body weight of at least 9 kg.
4. Has an LAR/caregiver capable of providing informed consent and able to attend all scheduled study visits, oversee the administration of study drug, and provide feedback regarding the study participant's symptoms and performance as described in the protocol.
5. Provides assent to the protocol (to the extent possible and in accordance with local institutional review board [IRB] and regulatory requirements) and has a LAR/caregiver who will provide written informed consent. Study participants providing assent must do so at the same visit as LAR/caregiver written informed consent is provided.
6. Can swallow study drug capsules with water or ingest the contents of study drug capsules after sprinkling the capsule contents onto up to 1 teaspoon of low-fat semiliquid food.

7. If a study participant is currently receiving a regimen of concomitant medications such as antiepileptic medication, gabapentin, clonidine, trazodone, melatonin, and/or a special dietary regimen, that study participant's regimen is stable for at least 4 weeks before Day 1 (first day of study drug administration) and will be maintained throughout the duration of the study (in the judgment of the investigator).
8. Has LAR/caregiver(s) who agree not to post any of the study participant's personal medical data or information related to the study on any website, message board, online support group, or social media site (e.g., Facebook, Instagram, Twitter) until notified that the study is completed.
9. Female study participants who are of childbearing potential (defined as having experienced their first menarche) must agree to use either a highly effective or acceptable form of birth control during the study and for 30 days following the last dose of the study drug. Highly effective contraceptive methods are as follows:
 - Combined (estrogen- and progestogen-containing) hormonal contraception associated with inhibition of ovulation:
 - Oral
 - Intravaginal
 - Transdermal

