4.1.2 Exclusion Criteria

Study participants meeting any of the following criteria will be excluded from the study:

10. Discontinued from the OV101-15-001, OV101-16-001, or OV101-19-001 study due to safety reasons causally related to OV101.
11. Has a circumstance, condition, concomitant disease (e.g., gastrointestinal, renal, hepatic, endocrine, respiratory, or cardiovascular system disease), or any clinically significant finding that could interfere with the conduct of the study or that would pose an unacceptable risk to the study participant in this study.
12. Has poorly controlled seizures defined as any of the following:
 - Weekly seizures of any frequency with a duration of more than 3 minutes each
 - Weekly seizures occurring more than 3 times per week, each with a duration of less than 3 minutes
 - Investigator assessment
13. Has any of the following laboratory abnormalities: total bilirubin $>1.5 \times$ upper limit of normal (ULN), unless known Gilbert's syndrome; alanine aminotransferase or aspartate aminotransferase $>2.5 \times$ ULN; serum creatinine $>1.2 \times$ ULN; absolute neutrophil count $<1.5 \times 10^9/L$; platelets $<80 \times 10^9/L$; hemoglobin $<80 \text{ g/L}$; or thyroid stimulating hormone $>1.25 \times$ ULN or $<0.8 \times$ lower limit of normal. Retesting of clinical laboratory parameters may be allowed after consultation with the medical monitor or designee.
14. Use of benzodiazepines, zolpidem, zaleplon, zopiclone, eszopiclone, barbiturates, or ramelteon for sleep, or minocycline or levodopa within the 4 weeks prior to Day 1 or during the study. Benzodiazepines administered as needed or regularly scheduled for indications other than insomnia and benzodiazepines for seizure control are permitted.
15. Is at risk of harming self and/or others (based on investigator assessment).
16. With the exception of an Ovid study of OV101, has enrolled in any clinical or used any investigational agent or device, or has participated in any investigational procedure, within the 30 days before screening or does so concurrently with this study.

17. Is allergic to OV101 or any excipients of study drug.
18. The study participant or LAR/caregiver is unable to comply with study requirements (based on investigator assessment).

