5.9.2 Restrictions

Any prior or concomitant medication, including antiepileptic and/or behavioral medications, supplements, or special diets, must be at a stable dose for at least 4 weeks before Day 1, and must be maintained throughout the study.

Benzodiazepines prescribed on an as-needed basis for situational anxiety (e.g., for occasional procedures or events) or scheduled for indications that are not related to sleep (e.g., seizures, anxiety) are permitted.

Study participants should not consume alcohol during the study.

6 Study Assessments and Procedures

Before submitting to any study procedures, all potential study participants and/or LAR/caregivers will sign an informed consent form (ICF). Study participants and LAR/caregivers will have the opportunity to have any questions answered before signing the ICF. The investigator must address all questions raised by the study participants and LAR/caregivers. The investigator or designee will also sign the ICF.

The schedule of activities by clinic visit for this study is presented in Table 6-1. Telehealth/virtual visits should be consistent with local and individual institutions' policies and standard practices. Detailed instructions for virtual/phone visits will be provided in the investigators' virtual/phone visit study manual. A home nurse visit will replace a virtual visit if the latter is not feasible.

Table 6-1 Schedule of Activities by Study Visit

Visit Name ^c	Screening ^a	Baseline ^b	Phone Titration	Week 12	Week 24 Telehealth/Virtual Visit ^p	Week 36	Week 48 Telehealth/Virtual Visit ^p	Week 64	Week 80 Telehealth/Virtual Visit ^p	Week 96	Week 112 Telehealth/Virtual Visit ^p	Week 128	Week 144 Telehealth/Virtual Visit ^p	EOT	EOS ^d (Phone)
Window (days)	– ^e	+1	+3	±7	±5	±7	±5	±7	±5	±7	±5	±7	±5	±7	±5
Day^f	–30 to -1	1	6, 11, 15	84	168	252	336	448	560	672	784	896	1008	1120	1134
Week	–	0	1-3	12	24	36	48	64	80	96	112	128	144	160	162
Obtain informed consent and assent	X														
Verify inclusion/exclusion criteria	X	X													
Obtain medical history and demographic information	X	X													
Conduct clinical assessment for AS ^g	X														
Confirm prior molecular AS diagnosis ^h	X														
Physical examination	X	X		X	X	X	X	X	X	X	X	X	X	X	
Vital sign measurements	X	X		X		X	X	X		X		X		X	
Clinical laboratory tests	X	X ⁱ		X		X		X		X		X		X	
Pregnancy test ^j	X ^j	X ^j		X ^j		X ^j		X ^j		X ^j		X ^j		X ^j	

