6.1 Study Visits

6.1.1 Screening Period

Study participants entering this study within 2 weeks of completing the EOT visit of OV101-19-001 do not need to have a screening period; the screening activities can be verified or conducted at the baseline (Day 1) visit. All other study participants will be screened for participation in the study up to 30 days before Baseline (Day 1), when the first dose will be administered. Study participants who meet all entry criteria can have their baseline clinic visit at any time during the screening period.

Written informed consent (from the study participant's LAR/caregiver) and assent (from the study participant) will be obtained before the study participant participates in any study procedure and begins the study screening procedures for eligibility. Assent will be obtained if the investigator believes that the study participant has the intellectual capacity to provide it, but assent may not be relevant based on the study participant's intellectual disability and/or age (Section 9.3).

Molecular confirmation of the diagnosis of AS was an inclusion criterion for OV101-15-001, OV101-16-001, and OV101-19-001. Blood tests for molecular confirmation of AS will not be performed unless the study participant is a sibling of a previous participant and does not have prior documented molecular confirmation.

During the screening period, the investigator will determine whether the LAR/caregiver and study participant are able to complete all questionnaires and assessments that require their contributions and will also assess their ability to comply with study procedures.

In preparation for participation in this trial, LAR/caregivers will be educated on the clinical safety data for OV101 obtained thus far and will be trained to report assessments and to identify, manage, and report any potential AEs.

The LAR/caregiver will be provided with a sleep diary for documenting the study participant's sleep and a seizure diary for documenting the study participant's seizures. The LAR/caregiver will record data in the sleep diary for at least 7 days before each clinic visit. A calendar reminder will also be provided for recording data in the sleep diary.

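### Section 5.9.1 bans regularly scheduled GABAergic agents from consent, but no exclusion criterion names them and other sections require stable regimens to continue, so an enrolled stable user of an unexempted agent cannot satisfy both rules

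*Combined protocol and SAP*

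**What the plan says.** **The prohibition.** Section 5.9.1: "Use of any GABAergic agents (e.g., acamprosate, baclofen, vigabatrin, tiagabine and riluzole) on a regular schedule is prohibited from the time informed consent is obtained". The ban lasts until the participant's participation ends. No washout is given, and nothing says what happens to someone already taking such an agent.

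**The stated exceptions.** Section 5.9.1 lets stable gabapentin continue. It also says: "Benzodiazepines administered as needed or as a regularly scheduled dose for indications other than insomnia (e.g., seizures, anxiety) are permitted". Exclusion criterion 14 and Section 5.9.2 repeat the benzodiazepine permission.

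**The eligibility rules.** Inclusion criterion 7 (Section 4.1.1) covers participants on concomitant regimens, with antiepileptics and gabapentin among its examples, on a condition that the investigator judges: "regimen is stable for at least 4 weeks before Day 1 (first day of study drug administration) and will be maintained throughout the duration". The drug-specific exclusion, criterion 14 (Section 4.1.2), covers benzodiazepines, zolpidem-type hypnotics, "barbiturates, or ramelteon for sleep, or minocycline or levodopa within the 4 weeks prior to Day 1 or during the study". It does not name vigabatrin, tiagabine, baclofen, acamprosate or riluzole. Criterion 18 excludes anyone the investigator judges unable to comply with study requirements.

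**The keep-stable rules.** Section 5.9.2 says that any prior or concomitant medication, antiepileptics included, "must be at a stable dose for at least 4 weeks before Day 1, and must be maintained throughout the study". Section 5.9 asks for stable regimens to be kept until after the end-of-study visit, with changes only to treat adverse events. It also lets the investigator give any medication judged necessary for the participant's welfare, without saying how that ranks against Section 5.9.1.

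**The concern.** The prohibited-medication rule was not carried into the eligibility criteria. Criterion 14 repeats the sleep agents, minocycline and levodopa from Section 5.9.1 with a look-back to Day 1, but the general GABAergic ban has no counterpart there. The written exceptions resolve the clash for two drug groups and leave it open for the rest.

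Three things are at stake.

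- **Consistency across sites.** The same candidate could be refused, enrolled with the medicine stopped, or enrolled with it continued.
- **Interpretation of seizure data.** The seizure diary starts at Screening for most participants (Section 6.2.2.4) and supplies the baseline for percent change in 28-day seizure frequency (Section 7.7.1). Section 6.2.1.1 makes a clear rise over the participant's baseline one trigger for recording seizures as an adverse event. Section 6.2.2.4 also says the calculated frequency will be used to confirm eligibility. In the Phase 2 study, seizure was more frequent on OV101 than on placebo (Section 1).
- **Participant safety.** A stable medicine might be stopped only because two sections disagree.

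**Working it through.** The plan states no figure on this point, and Section 7.4 says the sample size is not power-based. The check is a comparison of texts plus simple arithmetic.

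**1. Reading by drug group**

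| Group, taken on a regular schedule | 4.1.2 (drug-specific) | 5.9.1 | 5.9 and 5.9.2 | Result |
|---|---|---|---|---|
| Examples named in 5.9.1 (vigabatrin, tiagabine, baclofen, acamprosate, riluzole) | not named | prohibited from consent | keep unchanged | conflict once enrolled |
| Stable gabapentin | not named | permitted | keep unchanged | consistent |
| Benzodiazepines, not for insomnia | permitted | permitted | keep unchanged | consistent |
| Barbiturates for seizures | not caught (criterion 14 is limited to sleep) | no exception written | keep unchanged | unclear |

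The barbiturate row is unclear because Section 1 calls the study drug's action "unlike any other GABAergic agent, including benzodiazepines, zolpidem, zaleplon, zopiclone, barbiturates, neurosteroids" among others. That wording lists barbiturates as GABAergic, but it describes mechanism and does not define the scope of Section 5.9.1.

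For the first row the conflict does not depend on indication, because Section 5.9.2 covers any prior or concomitant medication. The effect on seizure data does depend on it: that needs the agent to be influencing seizures in the participant concerned, which is an assumption.

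**2. Options for a stable user of a first-row agent**

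- Not enrolling breaks no rule.
- Enrolling and continuing breaks Section 5.9.1.
- Enrolling and stopping at consent breaks the keep-stable wording and usually the 4-week rule (step 3).

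A regimen already changed at least 4 weeks before Day 1 raises no conflict.

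**3. Timing of a stop at consent**

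Inputs: screening runs from Day -30 to Day -1 with no Day 0 (Table 6-1), and stability is required for 4 weeks, or 28 days, before Day 1. With consent on Day -d, d days remain before Day 1. The condition d ≥ 28 with d ≤ 30 gives d = 28, 29 or 30, so 3 of 30 possible days.

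Direct rollovers from OV101-19-001 "do not need to have a screening period; the screening activities can be verified or conducted at the baseline (Day 1) visit" (Section 6.1.1). A rollover who consents on Day 1 has 0 such days. Their diary starts at Baseline, so there is no screening diary to disturb. Instead the stop would coincide with starting OV101, and the two could not be separated.

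**4. Illustrative size of a disturbed baseline**

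The documents give no inputs, so these are assumptions. A fraction f of the baseline (0.25 to 1.0) is recorded while the seizure rate is multiplied by m (1.25 to 2.0). The baseline, relative to the old level, is b = 1 + f(m − 1).

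- Rate later returns to its old level: apparent change = 1/b − 1. With f = 0.25 and m = 1.25, b = 1.0625 and the change is −5.9%. With f = 1 and m = 2, b = 2 and the change is −50.0%.
- Rate stays raised: apparent change = m/b − 1. With f = 1 it is 0% for any m. With f = 0.25 and m = 2, b = 1.25 and the change is +60.0%.

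All of this would arise with no effect of OV101, and in either direction.

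**5. Number affected**

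Not given. At an assumed 1% to 10% of 170 it is 1.7 to 17, about 2 to 17 participants. Zero is also possible.

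**The case against.** The strongest reply is that the rules can be read together. Criterion 7 admits a regimen only if it will be maintained. A medicine barred from consent cannot be, so the candidate fails criterion 7, and criterion 18 offers a second route. Eligibility is checked at Screening and Baseline. This stands. A reader might infer that no site can follow all the rules, and the documents do not support that: a site complies by not enrolling. But no text directs refusal, both routes rest on the investigator's judgment, and the welfare clause in Section 5.9 points the other way.

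A reader might also infer that every scheduled GABAergic medicine is caught, or that Section 5.9.1 contradicts itself on benzodiazepines. It does not. A general ban with specific written exceptions is coherent, and stable gabapentin and scheduled benzodiazepines for uses other than insomnia are expressly allowed.

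Third, no passage orders a medicine to be stopped at consent. That is one way a site might respond to the ban, so the timing and baseline results describe a possible consequence, not a planned procedure.

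Finally, most entry routes require completion of an earlier OV101 study whose medication rules are not in these documents, so few or no participants may be affected. Seizure frequency is summarised descriptively, and medication changes are recorded and listed by participant, so an affected baseline could be traced. These points lower the severity. They do not remove the conflict for the agents named without an exception.

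**Conclusion.** The contradiction is real but limited to regularly scheduled agents without a stated exception. For those agents, the keep and prohibit rules cannot both be met once a stable user is enrolled. The status of scheduled barbiturates for seizures is unclear.

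The timing result (3 of 30 days, or 0 for a rollover consenting on Day 1) follows from the protocol's own windows, but applies only if a site stops the agent at consent. The apparent changes in seizure frequency and the 2 to 17 participants rest entirely on assumed inputs. The documents do not establish that any participant is affected or that any baseline will be disturbed.

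The text is wrong as written. It calls for correction because it governs who enters and whether a stable medicine continues, but it does not undermine the planned analysis as a whole and does not rank with the most serious class of defect.

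A smaller slip belongs with it. The gabapentin exception counts its 4 weeks back from randomization, which this open-label study does not have, whereas criterion 7 counts from Day 1.

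**What to change.** The sponsor must reconcile inclusion criterion 7 in Section 4.1.1, the exclusion criteria in Section 4.1.2, and Sections 5.9, 5.9.1 and 5.9.2, together with the synopsis copies of the criteria. For each GABAergic class (the examples in Section 5.9.1, barbiturates, benzodiazepines, gabapentin), the eligibility, prohibited-medication and keep-stable rules should give one consistent answer. The revised text should also say how the welfare clause in Section 5.9 ranks against the prohibition. Which agents are allowed, and how current users are handled, is for the sponsor's clinical team to decide. The gabapentin reference to randomization must be reconciled with the Day 1 anchor in criterion 7.

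The cost is amendment wording in those sections and the synopsis, with no new procedures or data. Correcting only some of these places would leave a new inconsistency.

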5.9.2 Restrictions

Any prior or concomitant medication, including antiepileptic and/or behavioral medications, supplements, or special diets, must be at a stable dose for at least 4 weeks before Day 1, and must be maintained throughout the study.

Benzodiazepines prescribed on an as-needed basis for situational anxiety (e.g., for occasional procedures or events) or scheduled for indications that are not related to sleep (e.g., seizures, anxiety) are permitted.

Study participants should not consume alcohol during the study.

6 Study Assessments and Procedures

Before submitting to any study procedures, all potential study participants and/or LAR/caregivers will sign an informed consent form (ICF). Study participants and LAR/caregivers will have the opportunity to have any questions answered before signing the ICF. The investigator must address all questions raised by the study participants and LAR/caregivers. The investigator or designee will also sign the ICF.

The schedule of activities by clinic visit for this study is presented in Table 6-1. Telehealth/virtual visits should be consistent with local and individual institutions' policies and standard practices. Detailed instructions for virtual/phone visits will be provided in the investigators' virtual/phone visit study manual. A home nurse visit will replace a virtual visit if the latter is not feasible.

Table 6-1 Schedule of Activities by Study Visit

Visit Name ^c	Screening ^a	Baseline ^b	Phone Titration	Week 12	Week 24 Telehealth/Virtual Visit ^p	Week 36	Week 48 Telehealth/Virtual Visit ^p	Week 64	Week 80 Telehealth/Virtual Visit ^p	Week 96	Week 112 Telehealth/Virtual Visit ^p	Week 128	Week 144 Telehealth/Virtual Visit ^p	EOT	EOS ^d (Phone)
Window (days)	– ^e	+1	+3	±7	±5	±7	±5	±7	±5	±7	±5	±7	±5	±7	±5
Day^f	–30 to -1	1	6, 11, 15	84	168	252	336	448	560	672	784	896	1008	1120	1134
Week	–	0	1-3	12	24	36	48	64	80	96	112	128	144	160	162
Obtain informed consent and assent	X														
Verify inclusion/exclusion criteria	X	X													
Obtain medical history and demographic information	X	X													
Conduct clinical assessment for AS ^g	X														
Confirm prior molecular AS diagnosis ^h	X														
Physical examination	X	X		X	X	X	X	X	X	X	X	X	X	X	
Vital sign measurements	X	X		X		X	X	X		X		X		X	
Clinical laboratory tests	X	X ⁱ		X		X		X		X		X		X	
Pregnancy test ^j	X ^j	X ^j		X ^j		X ^j		X ^j		X ^j		X ^j		X ^j	

Visit Name ^c	Screening ^a	Baseline ^b	Phone Titration	Week 12	Week 24 Telehealth/Virtual Visit ^p	Week 36	Week 48 Telehealth/Virtual Visit ^p	Week 64	Week 80 Telehealth/Virtual Visit ^p	Week 96	Week 112 Telehealth/Virtual Visit ^p	Week 128	Week 144 Telehealth/Virtual Visit ^p	EOT	EOS ^d (Phone)
Window (days)	–^e	+1	+3	±7	±5	±7	±5	±7	±5	±7	±5	±7	±5	±7	±5
Day^f	–30 to -1	1	6, 11, 15	84	168	252	336	448	560	672	784	896	1008	1120	1134
Week	–	0	1-3	12	24	36	48	64	80	96	112	128	144	160	162
Adverse event inquiry	X	X	X	X	X	X	X	X	X	X	X	X	X	X	X
Concomitant medication inquiry	X	X	X	X	X	X	X	X	X	X	X	X	X	X	X
Assessment of suicidality: ABC-I ^a	X	X	X	X	X	X	X	X	X	X	X	X	X	X	X
Seizure diary issued SIF/DRF forms completed/submitted ^o	X	X		X		X		X		X		X	X		
Seizure diary review/collection		X		X		X		X		X		X	X	X	
Dispense medication diary		X		X	X	X	X	X	X	X	X	X	X	X	
Review/collect medication diary, assess compliance				X	X	X	X	X	X	X	X	X	X	X	
Dispense study drug		X		X	X	X	X	X	X	X	X	X	X	X	
Collect unused study drug				X	X	X	X	X	X	X	X	X	X	X	

Visit Name ^c	Screening ^a	Baseline ^b	Phone Titration	Week 12	Week 24	Week 36	Week 48	Week 64	Week 80	Week 96	Week 112	Week 128	Week 144	EOT	EOS ^d (Phone)
Window (days)	$-^e$	$+1$	$+3$	± 7	± 5	± 7	± 5	± 7	± 5	± 7	± 5	± 7	± 5	± 7	± 5
Day^f	-30 to -1	1	6, 11, 15	84	168	252	336	448	560	672	784	896	1008	1120	1134
Week	-	0	1-3	12	24	36	48	64	80	96	112	128	144	160	162
Clinician-Completed Measures															
VABS-3 ^k		X							X					X	
CGI-S-AS	X	X		X		X		X		X		X		X	
CGI-I-AS ^l				X		X		X		X		X		X	
Caregiver-Completed Measures															
CSHQ		X		X		X		X		X		X		X	
PedQoLI		X		X		X		X		X		X		X	
Sleep diary issued ^m	X	X		X		X		X		X		X			
Sleep Diary collected/reviewed		X		X		X		X		X		X		X	

Abbreviations: ABC-I, Aberrant Behavior Checklist-Irritability subscale; AS, Angelman syndrome; CGI-I-AS, Clinical Global Impressions-Improvement-Angelman syndrome; CGI-S-AS, Clinical Global Impressions-Severity-Angelman syndrome; CSHQ, Children's Sleep Habits Questionnaire; EOS, end of study; EOT, end of treatment; PedQoLI, Pediatric Quality of Life Inventory; VABS-3, Vineland Adaptive Behavior Scale, 3rd Edition.

Notes: At the investigator's discretion, study participants may be evaluated at unscheduled clinic visits for reasons related to study participant safety. At unscheduled visits, study participants will be queried about adverse events, changes in concomitant medications, and suicidality; and safety laboratory assessments may be conducted. Efficacy assessments will be only for study participants who are at least 4 years old. If study drug is dispensed at unscheduled visit, dosage should be maintained at the same level as at the previous scheduled visit. If a down-titration is required for a clinical indication, this must be discussed with the medical monitor prior to making the change or at the earliest opportunity. Up-titration should not be performed at an unscheduled visit.

^a For study participants entering this study within 2 weeks of completing the EOT visit of OV101-19-001, the screening activities can be verified or conducted at the baseline (Day 1) visit.

^b If the screening and baseline visits can be completed within 14 days, the following assessments do not need to be repeated at the baseline visit: medical history, clinical assessment, physical examination, clinical laboratory tests, and determination of concomitant medications. For study participants entering this study within 2 weeks of completing the EOT visit of OV101-19-001, the EOT visit activities need not be repeated.

^c If a study participant could not attend an in person visit, a telehealth/virtual or home visits, may be conducted by a trained mobile healthcare professional to perform study assessments e.g. vital signs, body system assessment, clinical labs draws, review/collection of study materials. Baseline visits must be conducted on site and not remotely for patients who did not complete an OV101 antecedent study (eg, siblings [with AS] of study participants with AS who have completed previous Ovid studies of OV101).

^d An ET study participant should complete both EOS and EOT visit assessments.

^e Screening is to be conducted for up to 30 days (inclusive) before Day 1; study participants who meet all entry criteria can start treatment at any time during the screening period.

^f There is no Day 0.

^g Signs and symptoms of AS.

^h Review documentation of previous molecular AS testing from the OV101-15-001, OV101-16-001 study, or OV101-19-001.

ⁱ If the baseline visit occurs within 14 days of the clinical laboratory tests during screening or during the study participant's EOT visit in OV101-19-001, clinical laboratory testing does not need to be performed at the baseline visit.

^j Serum pregnancy testing is to be completed at screening and baseline visits. At subsequent visits, urine pregnancy testing is performed.

^k The VABS-3 will be assessed by a trained qualified rater based on an interview of the study participant's caregiver. For each study site, the same rater is to be used throughout the study. As an exception, another sponsor-trained qualified rater in VABS-3 may be used.

^l Within 24 hours prior to the study participant's visit at Week 12 (the first CGI-I-AS assessment), the investigator must review the study participant's baseline CGI-S-AS score and investigator notes. Within 24 hours prior to the study participant's visit at Week 36 (and all subsequent visits with assessments of CGI-I-AS), the investigator must review the study participant's baseline CGI-S-AS score and investigator notes and the prior clinic visit's CGILAS score and investigator notes. The same clinician rater, trained in CGI-S-AS and CGI-I-AS rating by the sponsor, must be used throughout the study to assess a given study participant. It is recommended that the same rater be used at a given site. As an exception, a clinician sub-investigator, trained in CGISAS and CGI-I-AS rating by the sponsor, may be used.

^m The sleep diary is to be completed over the 7-day periods immediately preceding the clinic visits when sleep diaries are scheduled to be reviewed; a calendar will be issued to ensure that the diary information collection starts on the appropriate days. Phone calls to remind legally acceptable representative/caregivers to start recording diaries will be made 14 days before each study participant's expected next visit date.

ⁿ The entire Aberrant Behavior Checklist – Community (ABC-C) will be administered. Only ABC-I will be used to evaluate the potential for self-harm.

^o Seizure Identification Form and Diagnostic Review Form (SIF/DRF) will be completed by site personnel for every eligible study participant. This information will be faxed or emailed to The Epilepsy Study Consortium (TESC) for review and approval. The SIF/DRF will be used to ensure that the seizures are classified accurately. SIF and DRF forms will be collected for patients who have enrolled/completed the study if feasible.

^p A home nurse visit will replace a virtual visit if the latter is not feasible.

